9.4. Data Sources

The data will be recorded using an electronic case report form (eDCT) for each patient included. The completed eDCTs are the sole property of Pfizer and must not be provided to third parties in any format without the written approval of Pfizer, with the exception of authorized representatives of Pfizer or the appropriate competent authorities.

The treating physician is ultimately responsible for the collection and reporting of all clinical data, safety and laboratory data entered on the eDCTs and other forms for data collection (source documents) and must guarantee that they are accurate, authentic/original, traceable, complete, consistent, legible, timely (contemporaneous), permanent, and available as required. The eDCTs must be signed by the treating physician or authorized personnel. All corrections of entries on the eDCTs must be explained (reason for change) and signed off (electronic signatures) if available signature was broken. Corrections of entries are automatically recorded by the system (incl. date of change, user changing data, old and new value, reason for change). In most cases, the source documents are patient records in the hospital or at the doctor's office. In these cases, the data collected on the eDCTs must match the data in these records.

In some cases, the eDCT or part of the eDCT can also serve as a source document. In these cases, a document must be available at the doctor's study site and at Pfizer and must clearly identify the data recorded in the eDCT and for which the eDCT is considered a source document.

The clinical parameters recorded, especially those used to assess efficacy, are usual, known and recognized variables within each respective indication. All questionnaires used in the study have been validated.

9.4.1. Study Procedures

Consecutive subjects attending will be included if they fulfil all selection criteria for the study and are started on treatment with tofacitinib for moderate to severely active rheumatoid arthritis.

All visits shall be scheduled according to clinical practice. Within this study 4 visits may be documented and one follow-up telephone communication at least 28 days after the last clinic visit for those patients with an ongoing treatment-related AE should be conducted. At each visit subjects will undergo procedures in compliance with the country label and as per standard of care. In order to collect comparable study data, visits occurring +/- 14 days of the scheduled visit date can be documented. If a patient misses one or more pre-planned study visits the patient can remain in the study.

After a training session the sites will get access to the eDCT where the data and findings of the patient are documented. Also a folder with questionnaires will be provided. The collection of all data is prospective. Dose and duration of treatment should be based on clinical and individual needs and are determined by the treating physician. To provide accurate information of the treatment, the initial tofacitinib dose and all changes and the reasons for changes are documented during the course of the evaluation. The concomitant medication is determined by the treating physician and is registered in the eDCT.

9.4.2. Study Period

The planned observation period of each patient is 12 months. In this time period up to 4 visits will be documented.

9.4.2.1. Baseline Visit

Following parameters will be documented at baseline visit:

- Informed Consent.
- Demographic data.
- Educational level.
- Working status.

- Medical History including RA.
- Duration since diagnosis.
- Comorbidities.
- Co-medication.
- Inclusion/Exclusion criteria according to protocol and SmPC.
- Vaccination status for pneumococcus, influenza, herpes zoster and hepatitis B.
- Tuberculosis status.
- Hepatitis status.
- Prior drug treatment of RA.
- Concomitant drug treatment.
- Erythrocyte sedimentation rate (ESR).
- C-reactive protein (CRP).
- Serum rheumatoid factor (SRA).
- Cyclic Citrullinated Protein (CCP).
- Structural damage.
- Blood biochemistry & haematology.
- Number of swollen and tender joints.
- Morning Stiffness.
- Patient's Global Assessment of Arthritis.
- Physician's Global Assessment of Arthritis.
- Patients Assessment of Arthritis Pain.
- Health Assessment Questionnaire – Disability Index (HAQ-DI).
- EuroQol EQ-5D Health State Profile.
- Work Productivity and Activity Impairment (WPAI) Questionnaire.

- FACIT (Functional Assessment of Chronic Illness Therapy) – Fatigue.
- Patients' overall satisfaction with treatment.

9.4.2.2. Scheduled Visits 2- 3/Month 3 – Month 6

Following parameters will be documented at each interim visit:

- Adverse event monitoring.
- Concomitant drug treatment.
- Co-medication.
- Erythrocyte sedimentation rate (ESR).
- C-reactive protein (CRP).
- Blood biochemistry & haematology.
- Number of swollen and tender joints.
- Morning Stiffness.
- Patient's Global Assessment of Arthritis.
- Physician's Global Assessment of Arthritis.
- Patient's Assessment of Arthritis Pain.
- Health Assessment Questionnaire – Disability Index (HAQ-DI).
- EuroQol EQ-5D Health State Profile.
- Work Productivity and Activity Impairment (WPAI) Questionnaire.
- FACIT (Functional Assessment of Chronic Illness Therapy) – Fatigue.
- Medical visits to Rheumatologist and other specialists.
- Diagnostic test performed.
- Hospitalizations.

9.4.2.3. Final (or Close Out) Visit 4/Month 12

Following parameters will be documented at final visit:

- Adverse event monitoring.
- Concomitant drug treatment.

- Co-medication.
- Erythrocyte sedimentation rate (ESR).
- C-reactive protein (CRP).
- Blood biochemistry & haematology.
- Number of swollen and tender joints.
- Morning Stiffness.
- Patient's Global Assessment of Arthritis.
- Physician's Global Assessment of Arthritis.
- Patient's Assessment of Arthritis Pain.
- Health Assessment Questionnaire – Disability Index (HAQ-DI).
- EuroQol EQ-5D Health State Profile.
- Work Productivity and Activity Impairment (WPAI) Questionnaire.
- FACIT (Functional Assessment of Chronic Illness Therapy) – Fatigue.
- Patients' overall satisfaction with treatment.
- Medical visits to Rheumatologist and other specialists.
- Diagnostic test performed.
- Hospitalizations.
- Working status.

9.4.2.4. Patient Withdrawal

Subjects experiencing AEs as listed in the Xeljanz SmPC [with particular attention paid to Sections 4 (Contraindications), 5 (Special Warnings and 6 (Precautions)] should be monitored and if indicated, treatment should be withdrawn according to provision of the respective SmPC. If treatment with Tofacitinib or other DMARDs is withdrawn patients are followed up until the end of the observation period unless they withdraw from the study (see [Section 9.3](#)).

9.4.3. Schedule of Activities

The schedule of activities table provides an overview of the visits that may be documented. Refer to the **STUDY PROCEDURES** and **ASSESSMENTS** sections of the protocol for detailed information on each documentation and assessment.

According to his clinical practice the investigator may schedule visits (unplanned visits) in addition to those listed on the schedule of activities (SOA), in order to conduct evaluations or assessments required to protect the well-being of the subject. As this is a non-interventional study none of these visits are mandatory and every visit should be scheduled according to clinical practice.

Table 5. Schedule of Activities

Study Week	Baseline (Enrollment)	Month 3	Month 6	Month 12
Visit Number	1	2	3	4
Informed Consent	x			
Anamnesis/Medical History	x			
Demographic data	x			
Educational level	x			
Working status	x			x
Inclusion/exclusion criteria	x			
Vaccination status	x			
Treatment/Medication				
Prior RA drug treatment	x			
Concomitant RA drug treatment	x	x	x	x
Co-medication	x	x	x	x
Safety				
Inflammatory markers	x	x	x	x
Documentation of Comorbidities	x			
Documentation of AE		x	x	x
Efficacy				
Number of swollen and tender joints	x	x	x	x
Morning stiffness	x	x	x	x
Patients Global Assessment of Arthritis	x	x	x	x
Physicians Global Assessment of Arthritis	x	x	x	x
Patient Assessment of Arthritis Pain	x	x	x	x
Health Assessment Questionnaire – Disability Index (HAQ-DI)	x	x	x	x

Study Week	Baseline (Enrollment)	Month 3	Month 6	Month 12
Visit Number	1	2	3	4
EuroQol EQ-5D Health State Profile	x	x	x	x
Work Productivity and Activity Impairment (WPAI) Questionnaire	x	x	x	x
FACIT (Functional Assessment of Chronic Illness Therapy) – Fatigue	x	x	x	x
Overall satisfaction with treatment	x			x
Medical visits		x	x	x
Diagnostic tests		x	x	x
Hospitalizations		x	x	x

9.4.4. Assessments

9.4.5. Demographic Data

Demographic data will be documented at the Baseline Visit (Visit 1) including: date of birth, gender, weight, height, smoking status, alcohol intake.

9.4.6. Educational Level

Patient's educational level will be documented at the first visit (baseline visit).

9.4.7. Working Status

Patient's working status will be documented at the first (baseline visit) and the final visit (visit 4).

9.4.8. Medical History/Anamnesis

Patient's medical history will be documented at the first visit (baseline visit) including:

- RA diagnosis;
- Presence and level of RF and anti-citrullinated protein (ACPA) antibodies;
- Presence of erosions on x-rays;
- Presence of extra-articular manifestations (anemia, RA nodules, RA related vasculitis, amyloidosis or other).

9.4.9. Vaccination Status

At the Baseline Visit (Visit 1) current vaccination status of patients will be assessed for: pneumococcus, influenza, herpes zoster and hepatitis B.

9.4.10. Hepatitis and Tuberculosis Status

Hepatitis and tuberculosis status will be assessed at baseline visit (visit 1) according to the national guidelines.

9.4.11. Co-morbidities

At baseline visit (visit 1) the presence of co-morbidities will be documented. Co-morbidities of interest: cardiovascular disease, malignancies, infections, gastrointestinal disease (peptic ulcer and diverticulitis), osteoporosis, depression, hyperlipidaemia. For those co-morbidities present more information will be collected: year of diagnosis and treatment.

9.4.12. Prior and Concomitant Treatment

Relevant prior drug treatments will be recorded at the Baseline Visit (Visit 1). At each subsequent visit dose and route of administration of concomitant treatment will be documented.

9.4.13. Treatment of Rheumatoid Arthritis (RA-Treatment) with Tofacitinib and/or Other DMARDs

At each visit dose and route of administration (if applicable) of treatment with Tofacitinib and/or other DMARDs will be documented. In addition, stop date of previous DMARD(s), start date of new DMARD(s) and reason for switch (lack of efficacy or intolerance) will be documented.

9.4.14. Effectiveness Criteria

The effectiveness of the treatment with tofacitinib will be documented using, beside others, the following tools for the evaluation the course of the disease:

Table 6. Disease Activity Indicators

Indicator	Definition/Calculation
DAS28-4 (CRP)	$0.56*\sqrt{(TJC28)} + 0.28*\sqrt{(SJC28)} + 0.36*\ln(CRP \text{ in mg/l} + 1) + 0.014*\text{PtGA in mm} + 0.96$
DAS28-4 (ESR)	$0.56*\sqrt{(TJC28)} + 0.28*\sqrt{(SJC28)} + 0.70*\ln(\text{ESR in mm/ hour}) + 0.014*\text{PtGA in mm}$
Simplified Disease Activity Index (SDAI)	$(TJC28) + (SJC28) + [\text{PhyGA in cm}] + [\text{PtGA in cm}] + [\text{CRP in mg/dL}]$
Clinical Disease Activity Index (CDAI)	$(TJC28) + (SJC28) + [\text{PhyGA in cm}] + [\text{PtGA in cm}]$

TJC = tender joint count; SJC = swollen joint count; CRP = C-reactive protein in mg/L; ESR = erythrocyte sedimentation rate in mm/first hour, PtGA = Patient's global assessment of health; PhyGA = physician's global assessment of health

9.4.15. Joint Counts

9.4.15.1. Tender/Painful Joint Count (TJC28)

At each visit (visits 1-4) twenty-eight (28) joints will be assessed to determine the number of joints that are considered tender or painful. The response to pressure/motion on each joint will be assessed using the following scale: Present/Absent/Not Done/Not Applicable (to be used for artificial joints).

The 28 joints to be assessed are the shoulders, elbows, wrists, metacarpophalangeal (MCP) joints, proximal interphalangeal (PIP) joints, and knees. Artificial joints will not be assessed.

9.4.15.2. Swollen Joint Count (SJC28)

At each visit (visits 1-4) the joint assessor will also assess these joints for swelling using the following scale: Present/Absent/Not Done/Not Applicable (to be used for artificial joints).

The 28 swollen joint count includes the following joints: shoulders, elbows, wrists, metacarpophalangeal joints (MCP), proximal interphalangeal joints (PIP), and knees. Artificial joints will not be assessed.

9.4.16. Patient Assessment of Arthritis Pain

At each visit (visits 1-4) patients will assess the severity of their arthritis pain using a 100 mm visual analog scale (VAS) by placing a mark on the scale between 0 (no pain) and 100 (most severe pain), which corresponds to the magnitude of their pain.

9.4.17. Patient Global Assessment of Arthritis (PtGA)

At each visit (visits 1-4) subjects will answer the following question, “Considering all the ways your arthritis affects you, how are you feeling today?” The subject’s response will be recorded using a 100 mm VAS with 0= very well and 100=very poorly.

9.4.18. Physician Global Assessment of Arthritis (PhyGA)

At each visit (visits 1-4) the Investigator will assess how the subject’s overall arthritis appears at the time of the visit. This is an evaluation based on the subject’s disease signs, functional capacity and physical examination, and should be independent of the Patient’s Global Assessment of Arthritis. The Investigator’s response will be recorded using a 100 mm VAS with 0=no disease activity and 100= worst disease activity.

9.4.19. Morning Stiffness

At each visit (visits 1-4) the duration of morning stiffness should be determined by asking the following questions: “Over the last 2 days, when did you wake in the morning?” “Over the last 2 days, when were you able to resume your normal activities without stiffness?”

9.4.20. Health Assessment Questionnaire – Disability Index (HAQ-DI)

The HAQ-DI¹⁷ assesses the degree of difficulty a subject has experienced during the past week in 8 domains of daily living activities: dressing and grooming, arising, eating, walking, hygiene, reach, grip, and other activities. Each activity category consists of 2-3 items. For each question in the questionnaire, the level of difficulty is scored from 0 to 3 with 0 representing “no difficulty,” 1 as “some difficulty,” 2 as “much difficulty,” and 3 as “unable to do”. Any activity that requires assistance from another individual or requires the use of an assistive device adjusts to a minimum score of 2 to represent a more limited functional status. This questionnaire should be completed by the patient at each visit (visits 1-4) prior to any procedures being performed at the visit, if possible. The form should then be checked by the site staff for completeness.

9.4.21. EuroQol EQ-5D Health State Profile

The EuroQol EQ-5D Health State Profile¹⁸ is a copyrighted, patient completed instrument designed to assess impact on health-related quality of life in five domains: mobility, self-care, usual activities, pain/discomfort, and anxiety/depression. Additionally, scores from the five domains may be used to calculate a single index value, also known as a utility score. The validity and reliability of the EuroQol EQ-5D has been established in a number of disease states, including rheumatoid arthritis. This questionnaire should be completed by the patient at each visit (visits 1-4) prior to any procedures being performed at the visit, if possible. The form should then be checked by site staff for completeness.

9.4.22. Work Productivity and Activity Impairment (WPAI) Questionnaire

The Work Productivity & Activity Impairment Questionnaire (WPAI): Rheumatoid Arthritis is a 6-item questionnaire that is specific for rheumatoid arthritis and yields four types of scores: absenteeism, presenteesism (impairment at work/reduced job effectiveness), work productivity loss and activity impairment.¹⁹ WPAI outcomes are expressed as impairment percentages with higher numbers indicating greater impairment and less productivity.

9.4.23. Functional Assessment of Chronic Illness Therapy (FACIT) - Fatigue Scale

The FACIT – Fatigue Scale is a subject completed questionnaire²⁰ consisting of 13 items that assess fatigue. Instrument scoring yields a range from 0 to 52, with higher scores representing better subject status (less fatigue). This questionnaire should be completed by the patient at each visit (visits 1-4) prior to any procedures being performed at the visit, if possible. The form should then be checked by site staff for completeness.

9.4.24. C-reactive Protein (CRP)

The CRP shall be analysed by a local laboratory as per standard clinical practice and documented at each visit (visits 1-4). It will be used in the calculation of several efficacy parameters.

9.4.25. Erythrocyte Sedimentation Rate (ESR)

The ESR shall be analysed by a local laboratory and documented at each visit (visits 1-4). It will be used in the calculation of several efficacy parameters.

9.4.26. Overall Satisfaction with Treatment

Satisfaction with treatment will be assessed at baseline visit (visit 1) and at the final visit (visit 4) on a 5-point scale (where 0 = very dissatisfied and 4 = very satisfied) in response to the question “How satisfied are you with the drugs you received for your arthritis during the last year?”

9.4.27. Medical Visits

All Rheumatologist visits or medical visits to any other specialist made since the last visit related to the disease will be documented at visits 2-4.

9.4.28. Hospitalizations

RA-related and all-cause hospital admissions since the last visit will be documented at visits 2-4. Information collected will include number of days and reason for admission.

9.4.29. Diagnostic Tests

The number and type of diagnostic tests performed since the last visit will be documented at visits 2-4.

9.4.30. Safety Criteria

In contrast to the usual procedure for clinical trials in observational trials the treatment decision is independent of the protocol. Additionally selection criteria of patients at baseline are not as strict as for clinical trials. Thus, this study can provide new insights into the safety of Tofacitinib in routine care. All adverse events (AEs) that will occur during the observation period will be documented. Additionally, at the end of the observation both, the physician and the patient will be asked the general tolerability of the treatment with tofacitinib and reasons for premature discontinuation rates will be analysed.

9.5. Study Size

The primary objective of this study is to identify factors predictive of remission or LDA at month 6 of treatment. This will be investigated using a logistic regression model. For the purposes of the sample size, we will consider the LDA response rate.

Peduzzi et al suggest that such an analysis requires at least 10 events (ie, responders) per variable proposed in the model. The minimum number of subjects to include in the study can therefore be estimated using the following formula:

$$N = 10 k/p$$

where p is the smallest of the proportions of responders or non-responders in the population and k the number of covariates.

Based on the results of previous studies, eg, A3921187 we would expect an LDA response rate of 50% at 6 months and assuming that the primary analysis will include ten covariates, it will be necessary to observe 100 events in approximately 200 patients (ie, 100 events/0.50).

It is expected that the amount of missing data and drop-outs will be minimal in this study, so no allowance has been made for this in the sample size calculation.

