9.7.3. Efficacy Analysis

9.7.3.1. Primary Analysis

The primary analysis will investigate the potential role of several baseline clinical and biochemical parameters as independent predictive factors of remission or LDA at month 6 of treatment, assessed by DAS28-4 (CRP) <2.6 and DAS28-4 (CRP) <3.2, respectively and will be calculated as follows:

$$\begin{aligned} \text{DAS28-4 (CRP)} = & 0.56 * \sqrt{(\text{TJC28})} + 0.28 * \sqrt{(\text{SJC28})} + 0.36 * \ln(\text{CRP in mg/l} + 1) \\ & + 0.014 * \text{PtGA in mm} + 0.96. \end{aligned}$$

This will be investigated using logistic regression. The potential predictive factors that may be considered include:

- Age;
- Gender;
- Weight;
- Smoking history;
- Time (years) from RA diagnosis;
- Serology: RF, ACPA;
- Previous biologic DMARD use (number);
- Current concomitant treatment;
- Glucocorticoid dose;
- csDMARDs: number and dose;
- Acute phase reactants: ESR and CRP;
- DAS28-4 (CRP) score;
- HAQ-DI score;
- CDAI;
- Lipids (LDL);
- Hb levels.

The effect of each factor will firstly be tested with a univariate logistic regression model. All potential factors with a p-value resulting from univariate analysis less than 10% will then be included in a multivariate model, along with any factors considered important from a clinical point of view. Predictive factors and their interactions will be chosen using a backward (step-down) selection. Predictive factors chosen will be those which have a p-value less than 5%. In the case of a significant interaction, all individual components of the interaction will be “forced” in the model, whether they are statistically significant or not. It is anticipated that the primary model will include approximately ten covariates.

Full details, including methods for handling missing data, will be provided in the SAP. For the primary endpoints of remission or LDA, a non-responder imputation will be used for patients who have missing data at month 6.

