6.1.1. Primary Endpoints

The primary endpoints are the rate of remission and low disease activity (LDA) at month 6 of treatment. These are assessed using the 28-joint Disease Activity Score C-reactive protein (DAS28-4 (CRP)), which is a composite endpoint, calculated using 4 variables (represented by '-4' in the name).

Remission and LDA are defined as DAS28-4 (CRP) <2.6 and DAS28-4 (CRP) <3.2 , respectively.

The DAS28-4 (CRP) will be calculated as follows:

PFIZER CONFIDENTIAL

$$\text{DAS28-4 (CRP)} = 0.56 * \sqrt{(\text{TJC})} + 0.28 * \sqrt{(\text{SJC})} + 0.36 * \ln(\text{CRP}+1) + 0.014 * \text{PtGA} + 0.96$$

Where CRP is in mg/l, TJC = tender joint count, SJC=swollen joint count, ln = natural logarithm and PtGA is the Patient's Global Assessment of Health in mm.

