8.2.3.1. Analysis of the Primary Endpoints

The primary endpoints of rate of remission and LDA at month 6 will be analysed as outlined in [Section 8.1.1](#). The rate of remission and LDA will also summarised at each visit as outlined in [Section 8.1.4](#). Missing data will be imputed using the methods outlined in [Section 7](#).

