8.2.5. Summary of Analyses

Outcome	Analysis Set	Supports Protocol Objective Number	Subgroups	Statistical Method	Covariates/ Strata	Missing Data
Rate of Remission at Month 6	FAS	1	None	Logistic regression	Potential predictive factors outlined in Section 6.4	NRI
Rate of LDA at Month 6	FAS	1	None	Logistic regression	Potential predictive factors outlined in Section 6.4	NRI
Rate of Remission at Month 12	FAS	2	None	Logistic regression	Potential predictive factors outlined in Section 6.4	NRI
Rate of LDA at Month 12	FAS	2	None	Logistic regression	Potential predictive factors outlined in Section 6.4	NRI
EQ-5D	FAS	2	None	MMRM	Baseline score, timepoint fitted as a fixed effect and baseline by timepint interaction	MMRM
FACIT-Fatigue	FAS	2	None	MMRM	Baseline score, timepoint fitted as a fixed effect and baseline by timepint interaction	MMRM
WPAI	FAS	2	None	MMRM	Baseline score, timepoint fitted as a fixed effect and baseline by timepint interaction	MMRM

PFIZER CONFIDENTIAL

Final Version 1.0

28-Jan-2020

Page 33 of 36

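### N=200 supports at most ten LDA covariates at 50% response, with no margin; the remission model, also primary, is not sized, and neither model has a size limit

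*Protocol*

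**What the plan says.** Protocol 9.5 requires ten events per model variable and gives N = 10k/p, "where p is the smallest of the proportions of responders or non-responders in the population and k the number of covariates". It names its endpoint openly: "For the purposes of the sample size, we will consider the LDA response rate". With an expected LDA rate of 50% at six months it concludes, "assuming that the primary analysis will include ten covariates, it will be necessary to observe 100 events in approximately 200 patients". On missing data and drop-out it expects little, "so no allowance has been made for this in the sample size calculation".

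The analysis is wider than that calculation. SAP 6.1.1 states: "The primary endpoints are the rate of remission and low disease activity (LDA) at month 6 of treatment". SAP 8.2.3.1 sends both endpoints to the logistic regression of SAP 8.1.1, and the table in SAP 8.2.5 has a separate row for "Rate of Remission at Month 6".

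On model size, Protocol 9.7.3.1 says: "It is anticipated that the primary model will include approximately ten covariates". SAP 6.4 lists the candidate covariates. SAP 8.1.1 admits every factor that passes a 10% univariate screen, adds factors chosen on clinical grounds, and lets interactions compete in backward selection. It states no maximum.

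**The concern.** The ten-events rule is the study's only justification for its size. It is worked through for one endpoint, one response rate and one model size. Three things fall outside it:

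- the second primary endpoint, remission;
- any LDA rate other than 50%;
- any model that takes in more than ten terms.

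The primary result is the set of predictors that the two models select. If the plan is followed as written, either model can be fitted with fewer events per covariate than the protocol itself asks for, and neither document would flag it. Neither document plans to check how far the selected set depends on the particular sample.

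**Working it through.** **Inputs.** Rule N = 10k/p, k = 10, LDA rate 0.50 and no missing-data allowance (Protocol 9.5). Thresholds DAS28-4 (CRP) <2.6 for remission and <3.2 for LDA (SAP 6.1.1). Candidate list (SAP 6.4). No remission rate is given in either document, so 20%, 30% and 40% are used here as assumptions.

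**1. The plan's figure.** 10 × 10 / 0.50 = 200 patients and 200 × 0.50 = 100 events. It reproduces exactly.

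**2. Margin for LDA.** Since p is the smaller of the two proportions, it cannot exceed 0.50, and 200 is the smallest N the formula can give for ten covariates. The limiting count is 200 × min(p, 1 − p), and the number of covariates supported is that count divided by 10.

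| LDA rate | Limiting count | Per covariate, ten covariates | Covariates supported |
|---|---|---|---|
| 50% | 100 | 10.0 | 10 |
| 45% or 55% | 90 | 9.0 | 9 |
| 40% or 60% | 80 | 8.0 | 8 |

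**3. Remission.** A score below 2.6 is also below 3.2, so remission cannot be more frequent than LDA. If LDA is 50%, any lower remission rate gives fewer than 100 events.

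| Remission rate (assumed) | Events at N = 200 | Per covariate, ten covariates | Covariates supported |
|---|---|---|---|
| 40% | 80 | 8 | 8 |
| 30% | 60 | 6 | 6 |
| 20% | 40 | 4 | 4 |

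**4. Number of candidates.** SAP 6.4 gives age, gender, weight, smoking (counted once), disease duration, RF, ACPA, number of prior bDMARDs, two concomitant-treatment indicators, glucocorticoid dose, csDMARD number, csDMARD dose, ESR, CRP, DAS28-4 (CRP), HAQ-DI, CDAI, LDL and Hb. That is 20 before interactions. At 50% LDA (100 events):

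- 12 entering: 100 / 12 = 8.3 events each
- 15 entering: 100 / 15 = 6.7
- all 20 entering: 100 / 20 = 5.0, an upper bound on the problem

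**5. Loss of patients.** The Full Analysis Set (Protocol 9.7.1, SAP 5.1) leaves out patients with no post-baseline measurements. The limiting count is n × min(p, 1 − p), so a smaller n lowers it at every response rate when the loss is unrelated to response. As an illustration, an assumed 10% loss leaves 180 patients: 180 × 0.50 = 90 instead of 100 at 50% LDA, and 180 × 0.40 = 72 instead of 80 at 60% LDA.

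**The case against.** Sizing on LDA is a stated choice, not a slip. Protocol 8.1.1 lists one primary item covering remission or LDA, Protocol 9.7.3.1 speaks of a single primary model, and nothing promises ten covariates for remission. SAP section 4 says there are no formal hypotheses or decision rules. This removes any charge of concealment. It does not size the remission model, which SAP 6.1.1, 8.2.3.1 and 8.2.5 make primary.

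Protocol 9.5 also glosses events as responders when it introduces the rule. On that wording, 55% LDA gives 110 events, 11 per covariate, and only rates below 50% fall short. The formula defines p as the smaller proportion, so the two-sided reading follows the calculation actually used. The remission figures are the same on either wording, and the LDA shortfall close to 50% is modest.

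Screening at 10% followed by backward selection at 5% will probably shrink the model. SAP section 1 says the protocol's analyses are unchanged, so the expectation of about ten covariates still stands. A reader might infer from the candidate list that a 20-covariate model at 5.0 events each is planned. The documents do not support that: every candidate would have to enter. What stands is that an expectation is not a limit.

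Bootstrap validation is, fairly, a request about model checking and not a correction to the sample size. It is kept because the selected predictors are the primary result and a cap alone does not show how stable they are.

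**Conclusion.** The point holds as one of scope and margin. N=200 meets the protocol's rule for an LDA model of at most ten covariates at 50% response, and supports fewer at any other rate. It carries no event calculation for remission, where four to eight covariates are supported if the rate lies between 20% and 40%. That range is an assumption. The direction needs only the nesting of the two thresholds, LDA at the assumed 50%, and a remission rate below it. No text limits either model to what its events support.

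Stronger readings do not follow:

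- A reader might infer that 200 is miscalculated or that more patients are required. The figure is correct, and smaller models satisfy the rule at other rates.
- A reader might infer that falling below ten events shows the selected predictors to be unstable. Protocol 9.5 states a minimum count and says nothing about stability of selection.
- A reader might infer that counting missing outcomes as non-response must reduce the limiting count. It moves patients from one outcome group to the other, so its effect depends on the response rate, and no claim is made on it. What can be said is that no allowance was made, and that loss from the Full Analysis Set lowers the count under the assumption in the working.

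This should be corrected, but it does not threaten the conduct of the study.

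**What to change.** Keep N=200.

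1. **Protocol 9.5.** State that 200 patients support at most ten covariates for LDA at 50% and fewer at other rates. Give the number supported for remission over a stated assumed range, for example four to eight at 20% to 40%.
2. **Protocol 9.7.3.1 and SAP 8.1.1.** For each endpoint, limit the terms entering the multivariable model, interactions included, to the observed smaller outcome count in the analysed set divided by 10. Fix a priority order before the outcome data are analysed, to apply when more factors pass the screen than the limit allows.
3. **SAP 8.1.1.** Repeat the whole selection, from univariate screen to final model, in bootstrap resamples. Report selection frequencies and optimism-corrected performance for each endpoint.

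The cost is wording in three sections and some extra analysis code. Protocol 9.7 calls for an amendment if the change counts as a major modification of the primary analysis. The downside is a less favourable stated figure and a smaller remission model. No patients are added.
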